## 4.3 HSP Substudy Endpoints

The endpoints for the HSP substudy will be defined the same as the Primary and Secondary Endpoints for the main study. Results will be reported descriptively using summary statistics. No pre-specified hypothesis testing will be performed.

The following as-treated analyses will be performed using the Primary and Secondary Endpoint results from main study and HSP substudy subjects.

1. Results will be summarized separately for subjects that have time-averaged power settings of  $\geq 40$  Watts vs.  $< 40$  Watts in the left atrium.

## Clinical Investigation Plan

- Results will be summarized separately for subjects that have  $\geq 50\%$  vs.  $< 50\%$  of lesions in the left atrium with power settings  $\geq 40$  Watts.
- Results will be summarized separately for subjects that have  $\geq 25\%$  vs.  $< 25\%$  of lesions in the left atrium with power settings  $\geq 40$  Watts.

### 4.4 Additional Data

The following additional data will be collected and reported using only summary statistics and no hypothesis tests with pre-specified criteria will be performed. These descriptive endpoints will be reported separately for main study subjects and HSP substudy subjects. An as treated analysis will be conducted using the Additional Data as described in the SAP.

- Proportion of subjects who achieve acute procedural success during the initial ablation procedure, where acute procedural success is defined as confirmation of entrance block in all pulmonary veins after a minimum waiting period of 20-minutes.
- Proportion of subjects with successful first-pass PV isolation during the initial ablation procedure, defined as confirmation of entrance block in all pulmonary veins following the initial minimum waiting period of 20-minutes.
- Proportion of subjects who experience any adverse event (AE)
- Proportion of subjects who experience any serious adverse event (SAE)
- Proportion of subjects that experience any procedure- and/or ablation catheter-related adverse event (AE) throughout the 12-month follow-up period.
- Proportion of subjects requiring one or more repeat AF ablations at 12 months following the initial AF ablation procedure.
- Changes in EQ-5D-5L and AFEQT scores from baseline to follow up at 3, 6, and 12-months after the initial procedure.
- Procedure data, including but not limited to, ablation data, mapping data, usage of HD Grid, usage of Automark, target contact force, power setting data, procedure time, fluoroscopy time, total RF time, time to perform initial PVI, and ablation lesions performed in addition to PVI.
- Proportion of subjects treated for concomitant typical AFL with the TactiFlex SE catheter
- Proportion of subjects treated for typical AFL with no recurrent AFL at 3, 6 and 12 months.
- Proportion of subjects that received CTI ablation with the TactiFlex SE catheter.
- Proportion of subjects that received CTI ablation that achieved bi-directional block.
- Evaluation of procedure data to determine target contact force as assessed by AF/AFL/AT recurrence.
- Evaluation of the relationship between ablation power with time to perform initial PVI.

### 5.0 SUBJECT SELECTION AND WITHDRAWAL

#### 5.1 Subject Population

This clinical investigation will enroll male and female subjects who have drug refractory, symptomatic, paroxysmal AF. Subjects must meet all eligibility criteria and provide written informed consent prior to conducting any investigation-specific procedures not considered standard of care.

## Clinical Investigation Plan

### 5.2 Subject Screening and Informed Consent

#### 5.2.1 Subject Screening

Potential patients presenting at the clinical sites will be fully informed about the clinical investigation, following the established Informed Consent process (described in **Section 5.2.2**). Once a duly dated and signed Informed Consent form is obtained, the clinical investigation-specific screening procedures may begin.

The following assessments may need to be performed after obtaining consent and prior to the procedure, as part of the screening process (further described in **Section 6.0**):

- Verification that a left atrial thrombus is not present on the day of or within one day of the ablation procedure (required for all subjects after consent, prior to procedure).
- Measurements for LVEF and LAD within 180 days of procedure, if not documented prior to consent and/or is not standard of care at the site.
- Electrocardiographic documentation of an AF episode within 12-months prior to informed consent/enrollment, if not already available in the patient's medical records. Documented evidence of an AF episode may be provided by a 12-lead ECG, Holter monitor, TTM, ICM, permanent pacemaker, or patch cardiac monitor. Documented evidence of the AF episode must either be continuous AF on a 12-lead ECG or include at least 30 seconds of AF on other ECG devices. Other forms of electrocardiographic documentation may be accepted at the approval of the Sponsor's Medical Director.

Subjects must be screened for clinical investigation eligibility by a member of the site's clinical investigation team previously trained to the CIP and will be entered into a site-specific screening log.

In case the subject does not meet all inclusion criteria or meets any of the exclusion criteria, the subject is considered a screening failure. The Site Principal Investigator or the delegated clinical investigation personnel will record the screening failure in the hospital records and on a screening log.

Patients meeting general inclusion criteria and no exclusion criteria will be asked to sign an Informed Consent form if they wish to participate in the clinical investigation. These patients will also be entered into the screening log.

Subject data will be collected following enrollment into the clinical investigation.

#### 5.2.2 Informed Consent

A template informed consent form will be provided to each site by the Sponsor under separate cover for use in this clinical investigation. Site-specific language will be added to the template and approved by research personnel, the Sponsor, and governing IRB/EC prior for use in the trial.

The Investigator or his/her authorized designee (if applicable) will conduct the Informed Consent process, as required by applicable regulations and the center's IRB/EC. This process will include a verbal discussion with the subject on all aspects of the clinical investigation that are relevant to the subject's decision to participate, such as details of clinical investigation procedures, anticipated benefits, and potential risks of clinical investigation participation. Subjects must be informed about their right to withdraw from the clinical investigation at any time and for any reason without sanction, penalty or loss of benefits to which the subject is otherwise entitled. Withdrawal from the clinical investigation will not jeopardize their future medical care or relationship with the investigator.

## Clinical Investigation Plan

During the discussion, the Principal Investigator or his/her authorized designee will avoid any improper influence on the subject and will respect subject's legal rights. Financial incentives will not be given to the subject. Subjects may be compensated for time and travel directly related to the participation in the clinical investigation. The subject shall be provided with the Informed Consent form written in a language that is understandable to the subject and has been approved by the center's IRB/EC. The subject shall have adequate time to review, ask questions, and consider participation. The Principal Investigator or his/her authorized designee will make efforts to ensure that the subject understands the information provided. If the subject agrees to participate, the Informed Consent form must be signed and dated by the subject and thereafter by the person obtaining the consent prior to any clinical investigation-specific procedures. The signed original will be filed in the subject's hospital or research charts, and a copy will be provided to the subject.

Failure to obtain informed consent from a subject prior to clinical investigation enrollment should be reported to Sponsor within 5 working days and to the reviewing center's IRB/EC according to the IRB's/EC's reporting requirements.

If, during the clinical investigation, new information becomes available that can significantly affect a subject's future health and medical care, the Principal Investigator or his/her authorized designee (if applicable) will provide this information to the subject. If relevant, the subject will be asked to confirm their continuing informed consent in writing.

### 5.2.2.1 Special Circumstances for Informed Consent

The following individual populations will be excluded from participation in this clinical investigation:

- Individuals without legal authority are excluded from the study population.
- Individuals under the age of 18 or age of legal consent are excluded from the study population.
- Individuals unable to read or write are excluded from the study population.
- Pregnant or breastfeeding women are excluded from the study population.

### 5.2.3 HIPAA Authorization Requirement (US only)

In addition, an authorization for use and disclosure of the subject's protected health information, in accordance with the Health Insurance Portability and Accountability Act (HIPAA), must be obtained from the subject or their legally acceptable representative. This authorization may be part of the Informed Consent form, or a separate form.

## 5.3 Eligibility Criteria

### 5.3.1 General Eligibility Criteria

Assessment for general eligibility criteria is based on medical records of the site and interview with a candidate patient, and determination by the investigator. If some of the clinical and laboratory tests are not included in site standard tests, they must be done after written informed consent is obtained, but before the subject has an ablation catheter inserted into their vasculature for an ablation procedure. Potential specific examples of this include the tests noted in in **Section 5.2.1** (LVEF, LAD, presence of thrombus, and electrocardiographic documentation of an AF episode within the prior 12-month period).

## Clinical Investigation Plan

Patients must meet ALL of the inclusion criteria to undergo the study procedures. If ANY of the exclusion criteria are met, the patient is excluded from the clinical investigation and cannot undergo the study procedures.

### 5.3.2 Inclusion Criteria

A patient will be eligible for clinical trial participation if he/she meets the following criteria:

1. Plans to undergo a catheter ablation procedure due to symptomatic PAF that is refractory or intolerant to at least one Class I or III antiarrhythmic drug.
2. Physician's note indicating recurrent self-terminating AF
3. One electrocardiographically documented AF episode within 12-months prior to informed consent/enrollment. Documented evidence of the AF episode must either be continuous AF on a 12-lead ECG or include at least 30 seconds of AF from another ECG device.
4. At least 18 years of age
5. Able and willing to comply with all trial requirements
6. Informed of the nature of the trial, agreed to its provisions and has provided written informed consent as approved by the Institutional Review Board/Ethics Committee (IRB/EC) of the respective clinical trial site.

### 5.3.3 Exclusion Criteria

A patient will be excluded from enrollment in the clinical trial if he/she meets any of the following criteria:

1. Persistent or long-standing persistent atrial fibrillation
2. Active systemic infection
3. Known presence of cardiac thrombus
4. Hypertrophic cardiomyopathy
5. Arrhythmia due to reversible causes including thyroid disorders, acute alcohol intoxication, and other major surgical procedures in the 90-day period preceding procedure
6. Myocardial infarction (MI), acute coronary syndrome, percutaneous coronary intervention (PCI), or valve or coronary bypass grafting surgery within 90 days of procedure
7. Left atrial diameter > 5.0 cm measured within 180 days of procedure (echocardiography or CT)
8. Left ventricular ejection fraction < 35% measured within 180 days of procedure (echocardiography or CT)
9. New York Heart Association (NYHA) class III or IV
10. Previous left atrial surgical or catheter ablation procedure
11. Left atrial surgical procedure or incision with resulting scar (including LAA closure device)
12. Previous tricuspid or mitral valve replacement or repair
13. Heart disease in which corrective surgery is anticipated within 180 days after the procedure
14. Bleeding diathesis or suspected pro-coagulant state
15. Contraindication to long term anti-thromboembolic therapy
16. Presence of any condition that precludes appropriate vascular access
17. Renal failure requiring dialysis
18. Known sensitivity to contrast media (if needed during the procedure) that cannot be controlled with pre-medication

## Clinical Investigation Plan

19. Severe pulmonary disease (e.g., restrictive pulmonary disease, constrictive or chronic obstructive pulmonary disease) or any other disease or malfunction of the lungs or respiratory system that produces severe chronic symptoms
20. Women who are pregnant or breastfeeding
21. Presence of other anatomic or comorbid condition that, in the investigator's opinion, could limit the patient's ability to participate in the clinical trial or to comply with follow up requirements, or impact the scientific soundness of the clinical trial results
22. Patient is currently participating in another clinical trial or has participated in a clinical trial within 30 days prior to screening that may interfere with this clinical trial
23. Patient is unlikely to survive the protocol follow up period of 12-months after the procedure
24. Body mass index > 40 kg/m^2
25. Presence of other medical, social, or psychological conditions that, in the investigator's opinion, could limit the subject's ability to participate in the clinical investigation or to comply with follow-up requirements, or impact the scientific soundness of the clinical investigation results.
26. Individuals without legal authority
27. Individuals unable to read or write
28. Patients who have had a ventriculotomy or atriotomy within the preceding 4 weeks of procedure,
29. Patients with prosthetic valves,
30. Patients with a myxoma,
31. Patients with an interatrial baffle or patch as the transeptal puncture could persist and produce an iatrogenic atrial shunt
32. Patient unable to receive heparin or an acceptable alternative to achieve adequate anticoagulation
33. Stroke or TIA (transient ischemic attack) within the last 90 days
34. Stent, constriction, or stenosis in a pulmonary vein.
35. Rheumatic heart disease
36. Severe mitral regurgitation (regurgitant volume  $\geq$  60 mL/beat, regurgitant fraction  $\geq$  50%, and/or effective regurgitant orifice area  $\geq$  0.40cm^2).

### 5.4 Subject Enrollment

A patient is considered enrolled in the clinical investigation from the moment the patient provides written informed consent.

If subjects, enrolled into the clinical investigation, had an ablation procedure where the TactiFlex SE was used and are later found to have met at least one exclusion criterion or not all inclusion criteria after the ablation procedure, these subjects will continue follow-up in the clinical investigation and will be included in the analysis population. A protocol deviation must be completed on the applicable CRF. Such subjects identified prior to the index procedure should be identified as screen failures and a protocol deviation is not necessary.

#### 5.4.1 Enrollment of Medicare Beneficiaries

This clinical investigation will enroll Medicare beneficiaries that qualify based on the inclusion and exclusion criteria defined for this trial. This IDE clinical trial conforms to all standards of Medicare coverage requirements. The Risks and Benefits section (**Section 15.0**) describes how all enrolled subjects, including Medicare beneficiaries, may be affected by the device under investigation.

## Clinical Investigation Plan

The intended clinical benefit of the TactiFlex™ Ablation Catheter, Sensor-Enabled™ is to provide relief of drug-refractory recurrent symptomatic paroxysmal atrial fibrillation. Medicare beneficiaries are expected to experience similar clinical benefit and outcomes from commercially available ablation products. Drug-refractory symptomatic paroxysmal AF impacts 9% of the population of those aged > 65 years and with the aging of the U.S. population, this number is expected to increase. Medicare beneficiaries would benefit from participation in this study because AF increases their risk of stroke and this condition contributes to significant hospitalizations each year as well as death if left untreated. This study would enhance our existing knowledge of clinical solutions for catheter ablations in evaluating the safety and efficacy of the TactiFlex and congruence with the currently accepted medical guidelines for AF treatment.

Subjects enrolled in the clinical investigation are expected to be consistent with the Medicare population based on age and as such, the clinical investigation results are expected to be generalizable to the Medicare population.

### 5.4.2 Historically Under-Represented Demographic Subgroups

The Sponsor intends to implement FDA's guidance on sex-specific data in medical device clinical investigations to ensure adequate representation of women and other traditionally under-represented demographic subgroups in this clinical investigation. As noted in the guidance, some barriers to participation of women and ethnic minorities in clinical investigations have traditionally been:

- Lack of understanding about main obstacles to participation of such subgroups in clinical research
- Inclusion/exclusion criteria potentially not needed to define the clinical investigation population may unintentionally exclude specific subgroups
- Under diagnosis of disease etiologies and pathophysiology leading to under referral of demographic subgroups
- Avoidance of specific subgroups by investigators and Sponsors due to the perception that it takes more time and resources to recruit them
- Fear of fetal consequences (for female participants)
- Family responsibilities limiting women's ability to commit time for follow-up requirements

The Sponsor will take the following steps to ensure adequate representation of women and racial or ethnic minorities in this clinical investigation:

- Abbott will provide training to investigational site personnel to ensure adequate representation of these demographic subgroups
- Abbott will approach sites without bias or consideration for specific demographic subgroups
- Abbott will have informed consent materials in alternative languages and will work with sites and IRBs/ECs on recruitment materials

### 5.5 Subject Withdrawal

Each enrolled subject shall remain in the clinical investigation until completion of the required follow-up period; however, a subject's participation in any clinical investigation is voluntary and the subject has the

## Clinical Investigation Plan

right to withdraw at any time without penalty or loss of benefit. Conceivable reasons for discontinuation may include, but not be limited to, the following:

- Subject death
- Subject voluntary withdrawal
- Subject lost-to follow-up as described below
- Subject fails to meet all Eligibility Criteria (**Section 5.3**)
- Procedure is aborted prior to (ablation) catheter insertion
- Procedure is aborted prior to RF energy delivery
- Subject's follow-up is terminated according to **Sections 6.6.1-6.6.2**.

The Sponsor must be notified of the reason(s) for subject discontinuation. The site will provide this information to the Sponsor. Investigators must also report this to their respective IRB/EC as defined by their institution's procedure(s).

No additional follow-up will be required or data recorded from subjects once withdrawn from the clinical investigation, except for the status (deceased/alive).

In case of subject withdrawal of consent, the site should make attempts to schedule the subject for a final clinical investigation visit. At this final follow-up visit, the subject will undergo the assessments as outlined for an unscheduled visit in **Section 6.6.5** if the visit does not coincide with a scheduled follow-up visit.

Withdrawn subjects count towards the total enrollment at the site and will not be replaced by enrolling additional subjects.

### 5.5.1 Lost-to-Follow-up

If the subject misses two consecutive scheduled follow-up time points and the attempts at contacting the subject detailed below are unsuccessful, then the subject is considered lost-to-follow-up. Site personnel shall make all reasonable efforts to locate and communicate with the subject (and document these efforts in the source documents), including the following for each time an attempt was made to contact the subject:

- A minimum of two telephone calls on different days over the specified follow-up windows to contact the subject should be recorded in the source documentation, including date, time and initials of site personnel trying to make contact.
- If these attempts are unsuccessful, a letter (certified if applicable) should be sent to the subject.
- If a subject misses one or more non-consecutive follow-up contact time points, it will be considered a missed visit. The subject may then return for subsequent visits.
- If the subject misses two consecutive time points and the above-mentioned attempts at communicating with the subject are unsuccessful, the subject will be considered lost-to-follow-up.

**Note:** Telephone contact with General Practitioner, non-clinical investigation cardiologist or relative without the presence of the subject or indirect documentation obtained via discharge letters will not be considered as subject contact.

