### 3.1 Clinical Investigation Procedures and Follow-up Schedule

The visit schedule for subjects is shown in **Figure 5**. Once eligibility is confirmed, the subject will undergo a study ablation procedure for treatment of their PAF condition. A blanking period of 90-days will be employed after the initial ablation procedure, followed by a 9-month evaluation period. The total follow-up period will be for 12 months. Medication adjustments, cardioversions, and one repeat ablation procedure may be performed in the blanking period without being considered a primary effectiveness endpoint failure (repeat ablation for AF must be performed 31-80 days after the initial procedure). Subjects must be off Class I and III antiarrhythmic drugs (AADs) after the blanking period, unless clinically justified. Follow-up assessments will occur either in-person at the clinic or via phone contact after the procedure. The scheduled follow-up visits will occur before the patient leaves the hospital and then at 7-days (phone call), 5-weeks (phone call), 3-months (in-person visit), 6-months (phone call), and 12-months (in-person visit) after the initial procedure. The subject will be exited from the trial after completing their 12-month follow-up visit.

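### The lost-to-follow-up rule can close out a treated subject as early as day 42, before any post-blanking rhythm check, and states no way back for a subject who later reappears

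*Protocol*

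**What the plan says.** Protocol section 3.1 lists the contacts after discharge in order, beginning "7-days (phone call), 5-weeks (phone call), 3-months (in-person visit", then 6 and 12 months. Section 6.6.3 gives the windows: 7 ± 2 days, 35 ± 7 days, and a 3-month visit at day 91. At that visit the 12-lead ECG is taken and the TTM device is issued.

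Section 5.5.1 states the rule twice. Its opening sentence reads "If the subject misses two consecutive scheduled follow-up time points and the attempts at contacting the subject detailed below are unsuccessful", and the closing bullet repeats it: "If the subject misses two consecutive time points and the above-mentioned attempts at communicating with the subject are unsuccessful". The effort required for each attempted contact is also set out: "A minimum of two telephone calls on different days over the specified follow-up windows to contact the subject should be recorded", followed by "If these attempts are unsuccessful, a letter (certified if applicable) should be sent to the subject". Contact with a general practitioner, outside cardiologist or relative "without the presence of the subject or indirect documentation obtained via discharge letters will not be considered as subject contact". The only statement about coming back concerns a different pattern: "If a subject misses one or more non-consecutive follow-up contact time points, it will be considered a missed visit", after which the subject may return.

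Section 5.5, Subject Withdrawal, lists loss to follow-up among the possible reasons for discontinuation and then says: "No additional follow-up will be required or data recorded from subjects once withdrawn from the clinical investigation, except for the status (deceased/alive". Withdrawn subjects are not replaced.

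Section 5.7 says the study is complete once every enrolled subject has either had the 12-month visit or been withdrawn. Section 13.0 uses the same two end states.

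In the SAP, section 2.2.3 censors event-free subjects at the last time they were known to be event-free. Section 2.9 works from available data. Section 2.13 plans multiple imputation, best-case and worst-case analyses, with details redacted.

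**The concern.** The rule takes no account of where in follow-up the two misses fall. The earliest possible pair is two phone calls made inside the 90-day blanking period, when recurrence does not yet count. A subject hard to reach by phone in the first six weeks may still attend the 3-month or 12-month visit, and those visits carry the endpoint information.

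For effectiveness, a subject closed out at that stage with no earlier failure is censored before the evaluation period and adds nothing to the Kaplan-Meier estimate where it matters. If reasons for dropping out of contact relate to outcome, the censoring is informative.

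For safety, section 4.1.1 evaluates atrio-esophageal fistula, tamponade/perforation and pulmonary vein stenosis through 12 months. A subject who missed the day-7 call could also report a 7-day event later. Read literally, the text would leave such reports unrecorded.

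Section 3.2 cites section 5.5.1 as the safeguard against loss to follow-up, so the rule should not itself create missing data.

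**Working it through.** The documents show no attrition rate, power or alpha (the sample-size text is redacted), so there is no stated figure to reproduce. The check is window arithmetic plus a bound under stated assumptions.

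**1. Earliest date of closure** (windows from section 6.6.3)
- Day-7 window closes: 7 + 2 = day 9.
- Week-5 window closes: 35 + 7 = day 42. The second miss cannot be established before then, and section 5.5.1 sets no deadline for the letter, so day 42 is the earliest date.
- Gap to the nominal 3-month visit: 91 − 42 = 49 days. Section 6.6.3 gives that window as 91 + 14 and Table 4 as 91 ± 14; these should be reconciled. Even at Table 4's lower edge (day 77), day 42 is 35 days earlier.
- Follow-up remaining to day 365: 365 − 42 = 323 days at most.
- If the misses are week 5 and month 3, closure is possible from 91 + 14 = day 105, leaving 365 − 105 = 260 days.
- The 12-month window closes at 365 + 30 = day 395.

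**2. Effort before closure** (section 5.5.1)
Two time points × at least two calls = at least four calls, plus a letter, all unsuccessful.

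**3. Does closure stop data?**
- Section 5.5: loss to follow-up is a reason for discontinuation, and withdrawn subjects have only vital status recorded.
- Sections 5.7 and 13.0: a subject ends as completed or withdrawn. A lost subject has not completed, so only withdrawn remains.
- SAP section 3.3 names withdrawals and loss to follow-up separately, but both as early termination.

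Treating a lost subject as withdrawn is therefore the better reading, though it is nowhere stated outright.

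**4. Size** (assumptions: 1% or 3% of N = 305 lost early; observed freedom 60% among the rest)
- Each subject: 1/305 = 0.33 points.
- With L lost, worst case = 0.60 × (305 − L)/305; best case = [0.60 × (305 − L) + L]/305; width = L/305.

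| Assumed loss | L | Worst case | Best case | Width |
|---|---|---|---|---|
| 1% | 3 | 59.4% | 60.4% | 1.0 point |
| 3% | 9 | 58.2% | 61.2% | 3.0 points |

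- If lost subjects truly did 20 points worse (assumed), the estimate would be too high by 0.20 × L/305: 0.2 points at L = 3 and 0.6 at L = 9.
- Standard error grows by √(305/302) = 1.005 to √(305/296) = 1.015, that is 0.5% to 1.5%.

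**5. Could it change the result?**
Take an exact binomial test against the 50% goal in section 4.1.2, with an assumed one-sided 0.025. The smallest passing count is 171 of 305 (56.1%). At 60% observed, about 21 lost subjects (21/305 = 6.9%), all counted as failures, would be needed: 0.60 × 284 = 170.4, or 170 successes, one short. At 3% lost, the worst case of 58.2% still passes.

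**The case against.** Several stronger readings are tempting, and the case against them is sound.

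- **Two unanswered calls are enough.** They are not. Both conditions in section 5.5.1 must hold, with at least four failed calls and a letter, and sites must make all reasonable efforts.
- **The plan expressly ends data collection for lost subjects.** It does not. The data stop is worded for withdrawn subjects and exempts vital status. Protocol section 7.3.1 and SAP section 3.2 name last visit, death, end of participation and withdrawal as the ends of safety surveillance, but not loss to follow-up. Section 6.6.5 records data whenever a subject is seen at the study site outside a scheduled visit. This leaves an ambiguity that sites could resolve differently; sections 5.5, 5.7 and 13.0 still favour the restrictive reading.
- **Return is forbidden.** Section 5.5.1 permits it for non-consecutive misses and is silent on the rest.
- **Such a subject contributes nothing to effectiveness.** Someone who failed acute procedural success already counts as a failure. The analysis populations and the text around the Kaplan-Meier rule are redacted, so the handling of early losses cannot be fully seen.
- **The whole 1–3 points is avoidable.** That would need every unreachable subject to be fully recovered. A late returner would still lack the missed fortnightly TTM transmissions.

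One part of the defence does not stand: the planned sensitivity analyses bound the effect of missing data but do not replace data that could have been collected.

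**Conclusion.** The point holds as a correctable weakness in the follow-up rules. The conditions for loss to follow-up can be met from day 42, before any scheduled post-blanking rhythm check. The better reading then treats the subject as withdrawn and stops recording apart from vital status, and no way back is stated. Outcomes from a subject who reappears may therefore be lost. A reader might infer that outcomes will certainly be discarded or that the trial's conclusion is at risk; the documents support neither, since they give no rate of early loss or of reappearance.

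The size is unknown. At an assumed 1–3% early loss (3–9 of 305), the best-to-worst-case range widens by at most about 1–3 points. With an assumed 60% observed freedom and one-sided 0.025, that would not reverse the effectiveness result. The change is worth making because it is cheap and reduces both missing data and possible informative censoring.

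**What to change.** Amend section 5.5.1 for subjects who received RF with TactiFlex SE:
- Assign final lost-to-follow-up status only after the 12-month window closes (day 395).
- Until then, attempt every scheduled contact, treating earlier runs of misses as missed visits from which the subject may return.
- Record any later ECG, TTM, Holter or safety data, and use them in the endpoint analyses.

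Amend section 5.5 so that the data stop does not apply to subjects lost to follow-up. Leave it in place for withdrawal of consent and for the exits in sections 6.6.1 and 6.6.2 (screen failure, catheter not inserted, and no RF delivered after the 30-day safety follow-up). Confining the stop to consent withdrawal alone would conflict with those exits.

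Cost: a few extra calls per unreachable subject, and one protocol amendment with IRB/EC notification or approval under sections 10.3 and 12.1 at up to 40 sites. No new visits are needed.
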